2.3.2.3 Immunogenicity

Immunogenicity of Adalimumab as determined by the formation of anti-drug-antibodies (ADAs) will be assessed by using validated immunoassays. Immunogenicity data will be received as external source data for analysis.

Blood samples for immunogenicity (assessment of anti-adalimumab antibodies development) will be taken at specified time points as indicated in [Table 2-5](#)

Table 2-5 Blood collection schedule for ADA and PK samples

Study visits	Time/Week
Visit 2	Baseline
Visit 3	Week 2
Visit 4	Week 4
Visit 8	Week 12
Visit 14	Week 24
Visit 15	Week 36
Visit 16	Week 48
End of Study Visit	If applicable
Unscheduled Visit	If applicable

All samples were analyzed in a screening assay. Study samples with a result below the validated screening cut-point were negative for binding anti-adalimumab antibodies and will be reported accordingly. In the event of a positive result (result above the screening cut-point) the sample were additionally analyzed in a secondary confirmatory assay (specificity assay). In case the assay signal could be reduced after addition of excess of adalimumab beyond the validated confirmatory cut-point, a sample was reported as confirmed binding positive. In contrast, samples with a result above the screening cut-point in the screening assay but which were negative in the confirmatory assay were reported as negative.

A transient ADA response occurs where a post baseline positive ADA response occurs but is followed by a negative ADA response before the end of Treatment Period 1 or end of study visit.

The incidence of patients with neutralizing ADAs will be summarized by treatment arms.

2.3.2.4 Pharmacokinetic evaluations

No formal PK will be performed. The adalimumab trough serum levels will be assessed at the same time points as ADA to support the evaluation of immunogenicity. Thereby, the drug tolerance level of the ADA method (which was determined during method validation) can be compared with the determined drug levels.

2.4 Statistical method planned in the protocol

The following section outlines the statistical methods planned in the protocol.

2.4.1 Analysis of the primary endpoint

The following statistical hypotheses will be used to assess equivalence between GP2017 and US-licensed Humira® with regards to DAS28-CRP change from baseline at Week 12:

$H_0: |GP2017 - \text{Humira}^\circledR| \geq 0.6$ versus $H_1: |GP2017 - \text{Humira}^\circledR| < 0.6$

To address both EMA and FDA regulatory requirements for establishing therapeutic equivalence both 95% and 90% confidence intervals will be estimated and used to assess equivalence of DAS28-CRP change from baseline at Week 12.

Therapeutic equivalence in terms of DAS28-CRP will be concluded if the 95% (as required by EMA) or 90% (as required by FDA) confidence interval for the difference in DAS28-CRP change from baseline at Week 12 between the two treatment groups is completely contained within the interval [-0.6, 0.6]. This is statistically equivalent to calculating two independent one-sided tests at 2.5%/5% alpha level (one in each direction), of which both have to be successful.

A mixed-model repeated measures (MMRM) analysis will be performed for DAS28-CRP change from baseline up to Week 12 as the endpoint, including treatment, stratification factors (region, body weight category, prior systemic therapy), time, the interaction between time (visits) and treatment all as categorical variables, and baseline DAS28-CRP as a continuous variable in the model.

DAS28CRP CFB = treat + strata + time + (time*treat) + baseline DAS28CRP

In the case that the IRT and eCRF values of the stratification factors differ the correct definition of the stratification factors used for the primary analyses will be based on the clinical database.

MMRM is a standard approach to longitudinal analysis of continuous endpoints. Its roots bear into linear mixed modeling methodology and it is specified as a multivariate normal model of the longitudinal data. More specifically, this model includes a saturated visit-by-treatment structure for the mean. That is, time is considered as a factor rather than a continuous variable, and thus MMRM makes no assumption about trends over time. Traditional linear mixed models make further assumptions about the covariance of within/intra-patient observations, which can either originate from random effects or residual errors. With MMRM the covariance structure is specified only through the residual error term. The most flexible covariance matrix is unstructured, that is, all variance and covariance parameters are estimated. Therefore, an unstructured covariance matrix will be used for the analysis, and if the unstructured covariance matrix results in a lack of convergence, an appropriate covariance structure will be selected.

Mean change from baseline at Week 12, standard errors and the two-sided 95%/90% CI for the mean difference between GP2017 and US-licensed Humira® will be estimated from the model and the 95%/90% CI compared to the pre-specified equivalence margin of [-0.6; 0.6]. A 0.6 change in DAS28-CRP score is considered as no clinically meaningful difference by EULAR criteria (Table 2-2) and is therefore used as the equivalence margin limits [0.6,-0.6].

The primary analysis will be performed on the Week 12 Per-protocol set (W12 PPS), which is the most appropriate analysis set to use when testing for equivalence.

2.4.2 Analysis of the key secondary endpoint

Time-weighted averaged change from baseline in DAS28-CRP until Week 24 (standardized AUEC approach) will be calculated and analyzed using an ANCOVA.

The averaged change from Week 2 and Week 24 will be estimated by a time-weighted mean across visits. The weights are derived using the standard formula from the trapezoidal rule across the visits. Mean averaged change from baseline from Week 2 to Week 24, standard errors and the two-sided 95%/90% CI for the mean difference between GP2017 & and US-licensed Humira® will be estimated from the model and the 95%/90% CI compared to the pre-specified equivalence margin of [-0.6; 0.6].

Both 95% and 90% confidence intervals shall be estimated and used to assess equivalence of time-weighted averaged change from baseline in DAS28-CRP until Week 24. No imputation will be performed for missing components of the DAS28-CRP score or the computed AUEC value itself.

The key secondary analysis will be performed on the Study Period 1 Per-protocol set (SP1 PPS) which is the most appropriate analysis set to use when testing for equivalence.

2.5 Determination of sample size

2.5.1 Sample size calculation for the primary endpoint analysis

The sample size for this study is based on an expected difference of zero and common SD of 1.30 for the DAS28-CRP change from baseline at Week 12 (ReAct study), an equivalence margin of 0.6 and assumed loss of 20% patients from the per-protocol analysis set. A 0.6 change in DAS28-CRP score is considered as no clinically meaningful difference by EULAR criteria and is therefore used as the equivalence margin limits [-0.6; 0.6].

In order to fulfil FDA regulatory requirements for establishing therapeutic equivalence (e.g. using 90% confidence interval), a sample size of 154 patients per treatment group (to maintain overall 246 evaluable patients for the primary endpoint analysis) will have 95% power to test the equivalence between GP2017 and US-licensed Humira®.

In order to fulfil EMA regulatory requirements for establishing therapeutic equivalence (e.g. using 95% confidence interval), a sample size of 154 patients per treatment group (to maintain overall 246 evaluable patients for the primary endpoint analysis) will have 90% power to test the equivalence between GP2017 and US-licensed Humira®.

[figure not shown]
2.5.2 Power for analysis of key secondary endpoint

From [Burmester et al \(2014\)](#) the standard deviation of the change from baseline of the DAS28-CRP at 6 months, i.e. roughly Week 24, was observed as 1.5. This is comparable with the value of 1.3 found by [Burmester et al \(2014\)](#) for the Week 12 assessment. This matches well with [Wells et al \(2009\)](#) who found that the standard deviation of the DAS28-CRP was 0.9 to 1.0, which would mean a change from baseline measurement could be expected to have an SD of 1.4 times of the baseline SD (provided the baseline and post-baseline measurements were independent).

The time weight average is a weighted score of four change values where the weights sum to 1. The exact value of the SD for the time-weight average is unknown because it depends on both the days of each visit for each subject and the correlation between the individual measurements. However, a range for the SD can be estimated. Assuming each DAS28-CRP change from baseline value has a common SD of 1.4 then the lowest possible SD for the time-weighted average will occur if all four changes scores are independent and equally spaced, so that the weights are all 0.25, and this is then the same as taking an average of four independent random variables, and in this case the standard deviation of the time-weighted value will be $\frac{1}{2}$ of common SD, i.e. 0.7. At the other extreme the maximum of the weighted average occurs if each change score is perfectly correlated with the others. Then the specific values of the weights are irrelevant as the weighted average, will be the same as a single value of the change score, and hence will have an SD of 1.4.

[Figure 2-2](#) below shows the resulting power for different values of the SD for the time-weighted average with 246 evaluable patients when calculating both 90% and 95% confidence interval. It is clear that there is always sufficient power (at least 80%) to demonstrate equivalence using the 90% confidence interval, and that the power will also be sufficient using the 95% confidence interval.

Figure 2-2 Power of AUEC analysis for various common standard deviations

2.6 Randomization and stratification

Randomization will be stratified at baseline (Visit 2) by region, body weight and prior therapy. The stratification ensures balanced allocation of patients to treatment groups within the strata.

- The strata for body weight will be “body weight < 80 kg” or “body weight \geq 80 kg”. Stratification by body weight will be based on the weight assessment at Visit 2.
- The strata for region will be “RoW” and “Americas”.
- The strata for prior therapy are presented in hierarchical order and the option highest in hierarchy has to be chosen in case of more than 1 prior therapy scheme in the individual patient’s history.
 1. Prior treatment with biologic DMARDs (patient belongs to this strata even if treated with other synthetic DMARDs as well)
 2. Prior treatment with other conventional synthetic DMARDs”) patient belongs to this strata only if they did not receive prior treatment with biologic DMARDs),
 3. Prior treatment with MTX only

Considering the fact that the treatment arm assigned by the IRT cannot be revised for a patient if a wrong stratum was selected, the correct value of the stratification factor coming from the clinical database will be used for the statistical analyses. However, summaries and listing of patients randomized in the incorrect stratum will also be presented (see Section 4.3.1.1).

The stratification factors will be included as factors in the statistical methods described in Section 2.4.

2.7 Definitions of analysis sets

The following analysis sets will be used for this analysis.

The primary endpoint analysis will be based on W12 PPS, and will be repeated on SP1 FAS as sensitivity analysis.

The key secondary endpoint analysis will be based on SP1 PPS, and will be repeated on SP1 FAS as sensitivity analysis.

The analyses of Study Period 1 data will be based on SP1 FAS, SP1 SAF, SP1 PPS.

The analyses of Study Period 2 data will be based on SP2 FAS, SP2 SAF, SP2 PPS.

In addition to the study protocol defined objectives, the entire study data (i.e., from the randomization up to Week 48) will also be analyzed based on SP1 FAS, SP1 SAF, SP2 PPS.

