### **3      Investigational plan**

#### **3.1    Study design**

This study has a parallel-group, randomized, double-blind design and it is planned to randomize approximately 308 patients with moderate to severe active RA at approximately 110 study sites worldwide. A screening period of up to 4 weeks will be used to assess patient's eligibility. All patients must be on a stable dose of MTX at least 4 weeks prior to randomization and continue throughout the study on this dose.

[figure not shown]
At the baseline visit (Day 1, Visit 2); eligible patients will be randomized using a 1:1 ratio to one of the two treatment arms: GP2017 or US-licensed Humira®. Randomized patients will enter a 24-week treatment phase Study Period 1 and shall be treated with s.c. injection of either GP2017 or US-licensed Humira®. Study drug administration will be performed at the site by designated unblinded personnel. At Week 24 all patients will be evaluated for their DAS28-CRP response. Patients who did not show at least a moderate DAS28-CRP response will have their final assessment at Week 24 and will not continue in the study.

Irrespective of their treatment during Study Period 1, all patients with at least a moderate response at Week 24 by DAS28-CRP score, will be switched to or continue with subcutaneous injection of GP2017 from Week 24 up to Week 46. EoS Visit will be performed at Week 48.

In Study Period 2, all patients will self-administer GP2017 injections. At Week 24 (Visit 14), appropriate training for administration of GP2017 will be provided and first self-administration will be done under the supervision of designated unblinded study personnel at the study site. Afterwards, the patient will receive written Instructions for Use (IFU) of GP2017 and will self-administer GP2017 injections.

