At the baseline visit (Day 1, Visit 2); eligible patients were randomized using a 1:1 ratio to one of the two treatment arms: GP2017 or US-licensed Humira®. Randomized patients entered a 24-week treatment phase Study Period 1 and were treated with s.c. injection of either GP2017 or US-licensed Humira®. Study drug administration was performed at the site by designated unblinded personnel. At Week 24 all patients were evaluated for their DAS28-CRP response (based on CRP taken at Week 22). Patients who did not show at least a moderate DAS28-CRP response had their final assessment at Week 24 and did not continue in the study.

Irrespective of their treatment during Study Period 1, all patients with at least a moderate response at Week 24 by DAS28-CRP score, were to be switched to or continued with subcutaneous injection of GP2017 from Week 24 up to Week 46. End of Study (EoS) Visit was to be performed at Week 48.

2 Statistical and analytical plans

Data will be analyzed by Sandoz according to the data analysis described in Section 9 of the study protocol. Important details are given in the following sections, and the statistical methods will also be summarized as applicable in Appendix 16.1.9 of the CSR.

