2.3.1.4 EULAR response criteria

The EULAR good response, moderate response, and no response based on the DAS28-CRP are defined as follows.

Table 2-2 EULAR response criteria

Improvement in DAS28 from baseline			
Present DAS28	> 1.2	> 0.6 and ≤ 1.2	≤ 0.6
≤ 3.2	good response	moderate response	no response

Improvement in DAS28 from baseline			
Present DAS28	> 1.2	> 0.6 and \leq 1.2	\leq 0.6
> 3.2 to \leq 5.1	moderate response	moderate response	no response
> 5.1 (high)	moderate response	no response	no response

EULAR remission is defined as DAS28-CRP < 2.6.

If the DAS28-CRP is missing then the EULAR response is set to missing. Note that it is a condition of continuation into SP2 that a patient show at least a moderate response based on DAS28-CRP at Week 24 (using Week 22 CRP values).

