2.7.2 Per-protocol Set (PPS)

Week 12 Per-protocol analysis set (W12 PPS): consists of all patients in the SP1 FAS who complete Week 12/Visit 8 and do not have any major protocol deviations regarding the evaluation of the study's primary objective and have received at least 5 doses of IMP up to Week 10.

The major protocol deviations were defined in BDRM, refer to the BDRM minutes for the details (version final 1.0, dated 19-Mar-2018).

Study Period 1 Per-protocol set (SP1 PPS): consists of all patients in the W12 PPS who complete Week 24/Visit 14 and do not have any major protocol deviations regarding the evaluation of the study's key secondary objective and have received at least 5 doses of IMP from Week 12 to Week 22.

Study Period 2 Per-protocol set (SP2 PPS): consists of all patients in the SP1 PPS who complete the entire study (Week 48/Visit 16) and do not have any major protocol deviations during the entire study with regards to any efficacy assessment and have received at least 10 doses of IMP from Week 24 to Week 46.

As defined in the PPS definitions, in addition to major protocol deviations, patients who completed the required study visit but did not meet the study treatment compliance will also be excluded from the per-protocol sets:

- For W12 PPS, patients have to receive at least 5 doses of IMP up to Week 10. Patients should receive six doses of IMP from Baseline to Week 10 (i.e., Baseline, Week 2, 4, 6, 8, 10). A patient who completed Week 12 (i.e., Week 12 visit assessment is available in subject visit dataset) but missed 2 or more doses of IMP will be excluded from W12 PPS.
- For SP1 PPS, patients have to receive at least 5 doses of IMP from Week 12 to Week 22. Patients should receive six doses of IMP from Week 12 to Week 22 (i.e., Week 12, 14, 16, 18, 20, 22). A patient who completed Study Period 1 (based on disposition dataset) but missed 2 or more doses of IMP will be excluded from SP1 PPS.
- For SP2 PPS, patients have to receive at least 10 doses of IMP from Week 24 to Week 46. Patients should self-administrate twelve doses of IMP biweekly from Week 24 to Week 46 (i.e., the EPOCH variable equals to "Treatment Period 2" in study drug exposure dataset). A patient who completed the Study Period 2 (based on disposition dataset) but missed 3 or more doses of IMP will be excluded from SP2 PPS.

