2.7.3 Safety set (SAF)

Study Period 1 Safety set (SP1 SAF): consists of all subjects who received at least one dose of IMP, whether randomized or not. Subjects will be analyzed according to the treatment received.

Study Period 2 Safety set (SP2 SAF): The SP2 SAF set includes all SP1 SAF patients entering Study Period 2 who received at least one dose of IMP in Study Period 2.

3 Changes to planned analyses

Based on the study protocol Section 2.2, the efficacy evaluation of Study Period 2 includes calculating the changes from Week 24 at Week 48 for the following variables: DAS28-CRP, DAS28-ESR, HAQ-DI score, and FACIT fatigue score. In addition to changes from Week 24 at Week 48, the changes from baseline (i.e., randomization) at all applicable Study Period 2 visits will also be calculated and analyzed for above variables.

In addition to the study protocol defined objectives for SP1 and SP2 separately, the entire study data (i.e., from the randomization up to Week 48) will also be analyzed.

The SAP section “Power for analysis of key secondary endpoint”, more detailed information than in the study protocol are provided.

The protocol specifies no imputation for missing components of the DAS28-CRP score, because it was assumed that joint surgery would not occur. In accordance with general practice, the joints which not assessable throughout the study will be considered as not having tenderness or swelling (see Section 2.3.1.1).

4 Statistical analyses

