4.6.1.2 DAS28-CRP and DAS28-ESR scores

The change from baseline in DAS28-CRP and DAS28-ESR at all visits will be analyzed using the same MMRM method as for primary endpoint analysis (see Section 2.4.1).

DAS28-CRP and DAS28-ESR at baseline and weeks 2, 4, 12, 24, 36 and 48, and DAS28-CRP and DAS28-ESR change from baseline at weeks 2, 4, 12, 24, 36 and 48, will be summarized by treatment and visit using descriptive statistics. For DAS28-CRP and DAS28-ESR, the spaghetti plots by treatment and site will be provided, individual patient profile will also be provided.

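### The supplementary entire-study analysis on SP2 PPS selects patients on the outcome it reports: change from baseline is inflated, and the between-group difference is not a randomised comparison

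*SAP*

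**What the plan says.** **Sets.** SAP 2.7 says that, beyond what the protocol set out, "the entire study data (i.e., from the randomization up to Week 48) will also be analyzed based on SP1 FAS, SP1 SAF, SP2 PPS". Under SAP 2.7.2, SP2 PPS "consists of all patients in the SP1 PPS who complete the entire study (Week 48/Visit 16"), with no major deviation bearing on efficacy and at least 10 of the 12 Study Period 2 doses.

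**Entry to Study Period 2.** SAP 2.3.1.4 states: "it is a condition of continuation into SP2 that a patient show at least a moderate response based on DAS28-CRP at Week 24". The CRP result entering that judgement is the one from Week 22. Protocol 3.1 has the same rule, and the study design text in SAP Section 1 says that patients who fell short "had their final assessment at Week 24 and did not continue in the study". Response is itself defined from baseline. SAP Table 2-2 requires an improvement above 1.2, or above 0.6 with a present DAS28 of 5.1 or less.

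**What is analysed.** SAP Section 3 adds that "the changes from baseline (i.e., randomization) at all applicable Study Period 2 visits will also be calculated and analyzed" for DAS28-CRP, DAS28-ESR, HAQ-DI and FACIT-Fatigue. SAP 4.6.1.2 says that DAS28 change from baseline "at all visits will be analyzed using the same MMRM method as for primary endpoint analysis", without naming an analysis set.

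**Main analyses.** SAP 2.7 puts the primary endpoint on W12 PPS and the key secondary on SP1 PPS, each repeated on SP1 FAS. None of these sets requires a Week 24 response.

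**The concern.** Membership of SP2 PPS depends on DAS28-CRP improvement from randomisation at Week 24, and the entire-study analysis then reports improvement from that same baseline. Two things follow.

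- Mean change on this set is too large, including at Weeks 2 to 24, because patients who turned out to be non-responders have been removed in hindsight.
- If the products differ, the same response threshold removes different fractions of the two arms. What remains is no longer a randomised comparison.

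The SAP carries no caveat about this. It describes the per-protocol set as the conservative choice for equivalence when discussing W12 PPS (SAP 4.5). A reader could carry that reasoning over to SP2 PPS, where it does not hold. The overall summary columns (SAP 2.1.2) are also laid out by randomised arm through Week 48, which invites a 48-week product comparison.

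**Working it through.** **Plan's own figure.** The documents give no number for the SP2 PPS analysis. The nearest stated figure is the power with 246 evaluable patients (SAP 2.5.1). SE = 1.3 × √(2/123) = 0.166. Power = 2Φ(0.6/SE − z) − 1 gives 95.2% for the 90% CI and 90.3% for the 95% CI, against 95% and 90% stated. The design inputs are therefore internally consistent.

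**Simple bound.** If a fraction p with the poorest change is removed from a normal distribution with SD 1.5, the mean moves by 1.5 × φ(z)/(1 − p), where z = Φ⁻¹(1 − p).
- p = 0.10: 1.5 × 0.1755/0.90 = 0.29
- p = 0.30: 1.5 × 0.3477/0.70 = 0.75
- p = 0.40: 1.5 × 0.3863/0.60 = 0.97

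The 10% is an assumed low case. Protocol 3.2 cites 30-40%, but that covers anti-TNF failure or loss of response over time, not Week 24 non-response here. The sizes below therefore use the full EULAR rule instead.

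**Simulation, 600,000 patients per arm.**
- From the documents: SD of change 1.3 at Week 12 and 1.5 at Week 24 (SAP 2.5.1, 2.5.2); DAS28-CRP SD 0.95, the middle of 0.9 to 1.0 (SAP 2.5.2); the EULAR rule at Week 24.
- Assumed: baseline mean 5.7; Week 24 mean improvement 1.6, 2.0 or 2.4 in the better arm; Week 12 mean at 90% of that; Week 48 mean and SD equal to Week 24; within-patient correlations of change 0.6 to 0.7; baseline-change correlation −0.3. The Week 22 CRP substitution was not modelled.

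Mean change in the better arm, all patients → Week 24 responders, with the inflation in brackets:

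| Week 24 improvement | Kept | Week 12 | Week 24 | Week 48 |
|---|---|---|---|---|
| 1.6 | 70% | −1.44 → −1.87 (0.43) | −1.60 → −2.32 (0.72) | −1.60 → −2.10 (0.50) |
| 2.0 | 79% | −1.80 → −2.12 (0.32) | −2.00 → −2.54 (0.54) | −2.00 → −2.37 (0.37) |
| 2.4 | 86% | −2.16 → −2.39 (0.23) | −2.40 → −2.78 (0.38) | −2.40 → −2.66 (0.26) |

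Between-arm difference among responders when the true difference is a uniform 0.60:

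| Better arm's improvement | Kept, better / worse arm | Week 12 | Week 24 | Week 48 |
|---|---|---|---|---|
| 1.6 | 70% / 55% | 0.40 | 0.26 | 0.37 |
| 2.0 | 79% / 65% | 0.43 | 0.30 | 0.40 |
| 2.4 | 86% / 75% | 0.45 | 0.35 | 0.43 |

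Also dropping the worst 10% at Week 48, as a stand-in for completion, moves these differences by 0.03 or less. A second simulation (baseline 5.5, better-arm improvement 1.6 to 2.5, Week 12/24 correlation 0.7) gave 0.27-0.37 at Week 24 and 0.40-0.46 at Week 12.

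**Other patterns of difference** (all patients → responders):
- shift only among true responders: 0.30 → 0.30
- only more non-responders, 25% versus 40%: 0.36 → 0.02
- more non-responders but better responders: +0.12 → −0.30
- equal means, SD 1.3 versus 1.7: 0.00 → −0.28

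**The case against.** The strongest reply is that nothing turns on this analysis. It is declared as an addition, in a SAP to be finalised before unblinding, and no margin or equivalence conclusion is attached to it. It sits beside the same analysis on SP1 FAS. Protocol 9.5.2 asks for efficacy on both FAS and PPS, and the Study Period 2 objective openly restricts itself to patients with at least a moderate response. Change from Week 24 to Week 48, which avoids the problem of comparing different patients at the two visits, is already an endpoint. All of this stands and limits the weight of the point. It does not make Week 2 to 24 estimates unbiased in patients identified only later as responders.

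Three technical replies also stand in part.
- Entry is judged with Week 22 CRP, while the analysed Week 24 score uses Week 24 CRP (SAP 2.3.1.2). An SP2 PPS patient need not meet the threshold on the analysed score, and a sharp cut tends to overstate the selection. The other three components are the same Week 24 values, so the selection remains.
- No sentence ties the MMRM explicitly to SP2 PPS. That it would be run there is a reasonable combination of SAP 2.7, Section 3 and 4.6.1.2, but it is an inference.
- SP1 FAS is not a full cure after Week 24. Non-responders have no later data and a missing DAS28 is not imputed, so observed means there also come from responders. The MMRM on SP1 FAS does retain their values up to Week 24.

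**Conclusion.** The point holds as a limited one. On SP2 PPS, change from baseline is inflated by about 0.4-0.7 at Week 24, 0.2-0.4 at Week 12 and 0.3-0.5 at Week 48. The between-group difference is not a randomised comparison. For a uniform shift it moves toward zero, so that a true 0.6 becomes about 0.3 at Week 24 and 0.4 at Week 12. The sizes rest on the assumed means, baseline and correlations listed above, and on a sharp cut at Week 24. The direction of the inflation was the same in every run.

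Two stronger readings are tempting, and the documents do not support them.
- A reader might infer that selection shrinks any difference between the products. It need not: the bias can be nil, reversed or spurious. If the arms have the same distribution, as in the planned case of no difference, a common rule creates no difference.
- A reader might infer that the equivalence conclusion is at risk. It is not: the primary and key secondary analyses use sets that do not require a Week 24 response. At Week 48 both groups are on GP2017, so that contrast is continued versus switched treatment, not product against product.

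**What to change.** In SAP 2.7:
- Base entire-study change-from-baseline inference (the MMRM) on SP1 FAS.
- Take per-protocol comparisons up to Week 24 from W12 PPS and SP1 PPS.
- Restrict SP2 FAS and SP2 PPS to questions after Week 24, including change from Week 24.
- Present any retained change from baseline on the SP2 sets descriptively, with no between-product inference. Title it *Week 24 responders*, and for SP2 PPS add *who completed Week 48*.
- Footnote SP1 FAS by-visit summaries to say that observed means after Week 24 also come from responders only.

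The cost is SAP wording and some dropped or retitled tables; no new data are needed. The one loss is that no 48-week per-protocol between-group comparison of change from baseline would be reported.
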